### 3.2.3 Tolerability Endpoint

Participants will be judged tolerant of study drug if they reached their target dose and remain on study drug until planned discontinuation. Tolerability will be summarized as the proportion of participants in a treatment group who are tolerant of study drug.

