### **Rationale for the Study**

A significant body of literature from human neurophysiology studies of upper and lower motor neurons supports the hypothesis that neuronal hyperexcitability may contribute to neurodegeneration in both sporadic and familial ALS, and lower motor neuron excitability indices have been found prospectively to predict survival duration in recently diagnosed sporadic ALS patients. Data from the SOD1 mouse model also support this hypothesis, and now we have found that induced pluripotent stem cell-derived (iPSC) motor neurons from ALS patients are hyperexcitable compared to control-derived motor neurons. Based on the identified mechanism of reduced delayed-rectifier potassium channel currents (discussed below), we determined that the Kv7 agonist ezogabine (retigabine/Potiga) could reduce the *in vitro* motor neuron hyperexcitability. Consistent with the importance of hyperexcitability in the ALS disease process, we also found that ezogabine improved the *in vitro* survival of ALS-derived motor neurons, returning the survival to that of control-derived motor neurons. We now propose to determine how ezogabine affects neurophysiological measures of upper and lower motor neuron excitability in ALS patients as assessed by transcranial magnetic stimulation and threshold tracking nerve conduction studies, respectively, as such studies could be used as pharmacodynamic markers of a drug's effect on blocking motor neuron hyperexcitability. We will also draw subject blood samples to obtain and characterize iPSC-derived motor neurons from select trial subjects. Thus, a phase two trial investigating ezogabine in ALS patients could both evaluate a promising drug using neurophysiological excitability indices as pharmacodynamic monitors and serve as a proof of concept study for determining how iPSC-derived motor neurons might provide clinically relevant information with minimal time delay. Despite failed trials of multiple other anti-epileptics, ezogabine's unique mechanism combined with the strong preliminary data makes it an attractive candidate for the proposed translational study. Documentation of an effect on reducing hyperexcitability in ALS subjects, as well as

validating safety and determining dose, could pave the way for a larger trial to investigate effect on ALS using a combined measure of function/survival.

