### 3.2.2 Secondary Outcome Measures

Secondary outcomes include additional measures of efficacy and measures of safety, tolerability, pharmacokinetics, and *in vitro* response. Secondary efficacy outcomes include measures of upper and lower motor neuron excitability and measures of clinical progression. Motor evoked potential (MEP) threshold is the key secondary efficacy outcome, pre-specified for secondary efficacy analysis ahead of all other secondary efficacy outcomes. Additional upper motor neuron secondary outcomes include MEP amplitude, MEP latency, cortical silent period, and paired pulse facilitation, assessed by TMS. Lower motor neuron excitability outcomes include change in electrotonus, recovery cycle and strength duration time constant as determined by threshold tracking axonal nerve conduction studies (NCS) and compound motor action potential (CMAP) amplitude. The effect of retigabine on strength will be assessed using hand held dynamometry, and muscle symptoms (muscle cramps and fasciculations) will also be assessed utilizing a subject daily diary, in which the subjects will record the frequency, location and severity of their cramps over the course of study treatment.

Clinical progression outcomes include change in ALS Functional Rating Scale-Revised (ALSFRS-R) and slow vital capacity (SVC). Safety outcomes include adverse and serious adverse events, laboratory tests (including hematology, white cell differentials, blood chemistry, liver function tests, and urinalysis), weight loss, changes in electrocardiographic (ECG) parameters, changes in ophthalmologic parameters, and suicidality. Tolerability is defined as the proportion of participants able to reach their target dose and remain on study drug until planned discontinuation. Pharmacokinetic outcomes include peak concentration and time to peak concentration in serum and cerebrospinal fluid (CSF) after 2 weeks at target dose. *In vitro* exploratory outcomes include the following assessments of iPS-derived motor neurons: assessment of correlation between the primary clinical outcome (SICI using TMS) prior to treatment with ezogabine and the spontaneous firing rate of the *in vitro*-derived motor neurons; and correlation of the magnitude of the *in vivo* response to ezogabine detected by TMS and the *in vitro* EC50 for blocking motor neuron spontaneous action potential firing by ezogabine.

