#### **6.4 Modification of Study Intervention/Investigational Product for a Subject**

Any dosage adjustment, including the reason for and dates of adjustment, will be documented in the CRF for each subject requiring this manipulation. The SI or licensed physician Sub-Investigator may reduce the dosage of study drug or discontinue study drug in its entirety for AEs thought to be related to study drug or for other reasons during the trial (the reason for and dates of suspension or dose reduction must be documented). If the AE is mild or moderate, the dosage may be reduced until the event improves. The SI may then choose to resume the higher dosage or maintain the subject at a reduced dosage. Reference the study Manual of Procedures for additional information.

If the event is serious or life threatening and deemed to be definitely drug related, study drug will be discontinued immediately. Study subjects must remain off study drug permanently. Subjects may not resume study drug. The medical monitor should be notified immediately, preferably prior to any dosage adjustments, if possible.

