## **2.6 Treatment Administration**

Study drug will be orally self-administered in film-coated immediate-release tablets of a variety of strengths of ezogabine or matching placebo. In the 600 mg/day arm, ezogabine is titrated as follows: 100 mg TID for week 1, 150 mg TID for week 2, 200 mg TID for weeks 3 through 8, 200 mg BID for week 9, and 200 mg QD for week 10. In the 900 mg/day arm, ezogabine is titrated as follows: 100 mg TID for week 1, 150 mg TID for week 2, 200 mg TID for week 3, 250 mg TID for week 4, 300 mg TID for weeks 5 through 8, 200 mg BID for week 9, and 200 mg QD for week 10. In the placebo arm, participants receive a matching pseudo-titration of placebo tablets matched for size, color, and presentation.

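### The tolerability proportion counts as tolerant a participant who reached the target dose, was then reduced, and finished on a lower dose

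*SAP*

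**What the plan says.** The SAP defines the endpoint in section 3.2.3: "Participants will be judged tolerant of study drug if they reached their target dose and remain on study drug until planned discontinuation". The summary is a simple proportion by arm: "Tolerability will be summarized as the proportion of participants in a treatment group who are tolerant of study drug". Protocol 3.2.2 agrees: "Tolerability is defined as the proportion of participants able to reach their target dose and remain on study drug until planned discontinuation".

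Protocol 6.4 permits dose changes while a participant stays on drug. "If the AE is mild or moderate, the dosage may be reduced until the event improves", and afterwards "The SI may then choose to resume the higher dosage or maintain the subject at a reduced dosage". These changes are recorded: "Any dosage adjustment, including the reason for and dates of adjustment, will be documented in the CRF".

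SAP 2.6 sets the time at target. In the 900 mg/day arm it is "300 mg TID for weeks 5 through 8". In the 600 mg/day arm the target is reached in week 3 and held through week 8. Both active arms then taper in weeks 9 and 10.

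The Protocol Summary gives the purpose: an effect on excitability, together with "validating safety and determining dose, could pave the way for a larger trial".

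**The concern.** The definition asks whether the participant ever got to the target dose and whether the participant was still taking something at the end. It does not ask whether the participant could stay at the target. A participant who gets there, has side effects, is reduced and remains reduced passes both conditions and adds to the tolerability figure for a dose that was not sustained.

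The trial is meant to inform the dose for a larger study. For that decision the useful figure is the share of each arm that could take the assigned dose through the maintenance period. If lasting reductions are more frequent at one dose than at the other, the reported proportions could look more alike than the doses really are.

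**Working it through.** The documents state no expected tolerability rate and no sample size for this endpoint, so there is no figure to reproduce. The check applies the definition to each possible course and then counts.

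**1. Courses under the present rule**

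| Course | Reached target | On drug to planned end | Scored now | At target just before taper |
|---|---|---|---|---|
| Reduced or held during titration, never reaches target, stays on drug | no | yes | not tolerant | no |
| Reaches target, stops drug before the taper | yes | no | not tolerant | no |
| Reaches target and holds it | yes | yes | tolerant | yes |
| Reaches target, reduced, restored before the taper | yes | yes | tolerant | yes |
| Reaches target, reduced, not restored | yes | yes | **tolerant** | **no** |

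Only the last row is at issue.

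**2. Size in one arm**

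Inputs: n = 120/3 = 40 per arm (Protocol 4.1). D = participants who fail the present rule. R = participants in the last row. Neither D nor R is given in the documents.

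- Present rate = (n − D)/n
- At-target rate = (n − D − R)/n
- Overstatement = R/n, or 1/40 = 2.5 percentage points per participant

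With an assumed D = 8 (20%):

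| R | Present rate | At-target rate | Overstatement |
|---|---|---|---|
| 0 | 32/40 = 80% | 32/40 = 80% | 0 points |
| 2 (5%) | 80% | 30/40 = 75% | 5 points |
| 4 (10%) | 80% | 28/40 = 70% | 10 points |
| 8 (20%) | 80% | 24/40 = 60% | 20 points |

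The choice of D does not affect the difference. With R = 4, D = 4 gives 90% against 80%, and D = 12 gives 70% against 60%. The overstatement cannot be negative.

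**3. Comparison of the two doses**

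The 900-minus-600 difference shifts by (R900 − R600)/n. The rates below are assumed.

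| Reduced at 900 | Reduced at 600 | Shift in favour of 900 |
|---|---|---|
| 5% | 5% | 0 points |
| 10% | 5% | +5 points |
| 20% | 5% | +15 points |
| 5% | 10% | −5 points |

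The documents do not settle the direction. Protocol 2.2 reports dropout for adverse events of 20% at 900 mg/day and nearly 30% at 1200 mg/day in an earlier epilepsy study. That makes more reductions at the higher dose plausible, but it concerns dropout rather than reduction and does not compare 600 with 900. Against it, the 600 mg/day arm spends longer at target (weeks 3 to 8, six weeks) than the 900 mg/day arm (weeks 5 to 8, four weeks), which leaves more time for a reduction after target.

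**4. Whether another output isolates this group**

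- Time to discontinuation (SAP 3.10.2): a reduction is not an event.
- Compliance (SAP 3.10.2): doses taken over doses scheduled, with no link to holding the target. The SAP does not say whether the schedule is reset after a reduction.
- Adverse events by action on study drug (SAP 3.2.2 and 3.9.1): each participant is shown at the worst level, by arm. The levels are not listed. As described, the table does not separate reductions before target from those after it, or temporary from lasting. It also leaves out reductions made for reasons other than an adverse event, which Protocol 6.4 allows.

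**The case against.** The best defence is that this is a choice of definition, not an error. The two documents agree, the SAP speaks of tolerance of study drug rather than of a dose, and retention after reaching target is a legitimate measure. The proportion is descriptive, with no test on it. Reductions tied to adverse events should appear by arm in the action-taken table, and exposure days and compliance are reported too, so a reader choosing a dose would not see this proportion alone. All of that stands, and it limits the weight of the point. It does not supply the missing figure, because none of those outputs isolates participants who lost the target dose and stayed on drug.

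One might also say that the SAP's safety and tolerability sample groups people by the treatment actually received (SAP 3.5). Nothing there says that a later reduction moves a participant to another arm.

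Three stronger readings are tempting and are not supported:

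- **That only stopping the drug counts as intolerance.** Failing to reach target also fails the endpoint.
- **That the endpoint cannot tell 600 from 900 mg/day.** A participant in the 900 mg/day arm who never gets beyond 600 mg/day is scored not tolerant, while one on the same dose in the 600 mg/day arm can pass. The rule can mask a difference that arises after target; it does not remove the contrast.
- **That reduction is the protocol's first response to side effects.** Protocol 6.4 permits it, alongside discontinuation, and lists a return to the higher dosage as an option. It refers to the Manual of Procedures, which is not available here, for further detail.

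**Conclusion.** The point holds in a limited form. On the plain wording of SAP 3.2.3 and Protocol 3.2.2, a participant reduced after reaching target who finishes on a lower dose is counted as tolerant in the assigned-dose group. The resulting overstatement is R/n, zero if no such reduction occurs and 0 to 20 percentage points over an assumed rate of 0% to 20%. The documents give no rate, so no single figure can be attached. That the 900 mg/day arm is affected more than the 600 mg/day arm is plausible but assumed. The correction is worth making because the dose comparison is a stated purpose and the necessary data are already collected.

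**What to change.** In SAP 3.2.3, before unblinding, make the headline figure the proportion in each arm who meet all three conditions:

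1. reached the assigned target dose;
2. were on it on the last scheduled day before the planned taper, that is, the end of dosing week 8;
3. remained on study drug until planned discontinuation.

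Take condition 2 from the dose-change dates in the CRF, not from the Week 8 visit. That visit is on Day 56 ± 3 (Protocol 8.6), so Days 53 to 59. Counting from a first dose on Day 0, dosing week 8 covers Days 49 to 55, so the visit can fall after the taper has begun. Condition 3 keeps a participant who stops during weeks 9 or 10 from being scored tolerant.

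Count a participant whose reduction was reversed by that day as at target, and report separately by arm the proportion with any temporary reduction. Keep the present proportion (reached target and still on any study drug) as a second line, so that the gap between the two can be read directly.

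The planned taper must not be read as a reduction. The taper amounts for the 900 mg/day arm need reconciling in any case. SAP 2.6 gives 200 mg per dose in weeks 9 and 10, while the tablet configuration in Protocol 6.3 makes the 300 mg tablet the active one in that arm.

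Cost: a few sentences in the SAP and one or two more reported lines. No new data are needed, since dosage changes are already recorded with dates and reasons (Protocol 6.4) and are reportable within 24 hours (Protocol 11.3). The SAP governs on matters of analysis (SAP 1). The drawback is that the headline tolerability figure may fall.

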## 3.3 Measurement Definitions

### 3.3.1 TMS Measures

Transcranial magnetic stimulation (TMS) is a neurophysiologic test for assessing upper motor neuron function. A magnetic coil is positioned on the head above the motor cortex at a location that causes excitation of the abductor pollicis brevis (APB) muscle in a participant's dominant hand. High-frequency sampling of motor evoked potentials (MEP) in the APB is used to record neurophysiologic response to specific magnetic field strengths and sequences. The MEP traces are used to calculate a range of derived measures. MEPs that were below the limit of detect and recorded as zero mV were replaced by 0.005 mV.

- Resting motor threshold (RMT): RMT is the magnetic field strength, measured as a percentage of the maximum stimulator output, that produces at least a 0.05 mV response in at least 5 of 10 consecutive trials.
- MEP amplitude: MEP amplitude is defined as the response when a stimulus equal to 120% of RMT is administered. MEP amplitude is calculated as the geometric mean of replicate estimates.
- Short-interval intracortical inhibition (SICI): Paired-pulse SICI is defined as the ratio of the response after a conditioning pulse equal to 80% of RMT is administered 3 ms prior to the signaling pulse divided by MEP amplitude. SICI is calculated as the geometric mean of replicate estimates.
- Intracortical facilitation (ICF): Paired-pulse ICF is defined as the ratio of the response after a conditioning pulse equal to 80% of RMT is administered 15 ms prior to the signaling pulse divided by MEP amplitude. ICF is calculated as the geometric mean of replicate estimates.
- Cortical silent period (CSP): CSP is the suppression of voluntary muscle contraction elicited by stimulation equal to 120% of RMT. CSP duration is measured from the time of the muscle activity suppression to return of muscle activity.
- Input/Output curve parameters: MEPs elicited by stimuli ranging in strength from 60% of RMT to 150% of RMT follow a sigmoidal curve with upper and lower thresholds and a smooth, symmetric transition between the thresholds. A four-parameter logistic function fit to the input/output curve after log-transformation of output potentials yields estimates of maximum amplitude, minimum amplitude, midpoint of activation, and slope at the midpoint of activation.
- TMS quality: Good vs. poor quality TMS assessments will be evaluated as a measure of electrophysiologic response. Good quality will be defined as a central reader's evaluation that the TMS records were of good quality overall and that individual measurements of RMT, input/output curves, and CSP were of good quality.

TMS tracings were centrally reviewed and processed. Central readers indicated the reliability of the overall TMS assessment and of individual measures using a set of quality flags. Only TMS assessments that were evaluated as good quality overall and for measurement of RMT, input/output curves, and CSP are used for primary analysis. CSP times equal to zero were considered low quality whether flagged as such or not.

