## 3.5 Analysis Samples

The following analysis samples will be used for testing safety, tolerability, and efficacy endpoints:

- Safety and Tolerability (ST) Sample: ALS participants who are eligible, randomized, and take at least one dose of study drug, classified according to the actual treatment received. Observations made after premature permanent discontinuation of study drug are included in this sample, should such participants remain on study.
- Efficacy Modified Intent-to-treat (mITT) Sample: ALS participants who are eligible, randomized, and take at least one dose of study drug, classified according to their randomized treatment assignment. Observations made after premature permanent discontinuation of study drug are included in this sample, should such participants remain on study.
- Efficacy Per-protocol (PP) Sample: ALS participants who are eligible, randomized, and take at least one dose of study drug, classified according to the actual treatment received. Observations made after premature permanent discontinuation of study drug (whether due to intolerance, early termination, loss to follow-up, or death) are excluded from this sample.

- Efficacy Low RMT (loRMT) Sample: ALS participants and observations in the PP sample with RMT less than 67% of maximum stimulator output. This criterion ensures that the full TMS input/output curve could be conducted.
- Efficacy All Quality (AllQual) Sample: ALS participants and observations in the PP sample with no restriction that TMS quality is good.

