### 3.8.2 Secondary Analyses of the Primary Efficacy Endpoint

Several secondary analyses will be investigated to assess sensitivity of our estimates of treatment effect to alternative modeling assumptions.

- Active vs. placebo: A secondary estimand of the efficacy of ezogabine will compare both 600 mg/day and 900 mg/day treatment arms vs. placebo, tested at alpha = 0.05. The following SAS code specifies the linear contrast for this comparison:

```
estimate "2|ActvsPlb|dAvg 6&8"
  post*ttrrnd*visit 2 2 0 -2 -2 0 -1 -1 0 1 1 0 -1 -1 0 1 1 0 / cl divisor=4;
```

- Random-slopes model: The visit-specific fixed effects will be replaced with a continuous predictor of month since treatment initiation. Data from Final Safety and Early Termination visits will be placed at their observed follow-up time. Only assessments completed through Week 10, the end of planned study drug exposure, will be included. The following SAS code specifies the model and the linear contrasts used to estimate treatment-dependent differences in rate of change per month:

```
proc mixed data=xxx method=reml;
  where visit in ("Screening","Baseline","Week 04","Week 06","Week 08","Week 10");
  class site id ttrrnd;
  model Value = month ttrrnd*month;
  random intercept / subject=site type=vc;
  random intercept month / subject=id(site) type=un;
estimate "2|600vsPbl|Slope/mn" intercept 0 month 0 ttrrnd*month -1 1 0 / cl;
estimate "2|900vsPbl|Slope/mn" intercept 0 month 0 ttrrnd*month -1 0 1 / cl;
estimate "2|ActvsPbl|Slope/mn" intercept 0 month 0 ttrrnd*month -2 1 1 / cl divisor=2;
```

- Shared-baseline mixed model with pMI for missing data: The shared-baseline mixed model with fixed effects for visits described above for the primary analysis will be applied to datasets generated by placebo multiple imputation (Ayele et al. 2014). Fifty imputed datasets will be generated for a given endpoint.
- PP sample: The primary efficacy model and the secondary random-slopes model and active vs. placebo estimand will be applied to the PP sample.
- loRMT sample: The primary efficacy model and the secondary random-slopes model and active vs. placebo estimand will be applied to the loRMT sample.

- AllQual sample: The primary efficacy model and the secondary random-slopes model and active vs. placebo estimand will be applied to the AllQual sample.

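### No planned analysis gives the mITT, as-randomised estimate on all recorded SICI and RMT values, because the only sample without the TMS quality filter sits inside the per-protocol sample (minor)

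*SAP*

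**What the plan says.** The quality rule is in SAP 3.3.1: "Only TMS assessments that were evaluated as good quality overall and for measurement of RMT, input/output curves, and CSP are used for primary analysis". It adds an automatic failure: "CSP times equal to zero were considered low quality whether flagged as such or not". The unit removed is the whole assessment, so SICI and RMT leave together even if only the cortical silent period (CSP) or the input/output curve failed. For nerve conduction (SAP 3.3.2) the rule differs: once the overall flag passes, acceptability is judged by group of measures.

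The same section gives the indicator a second role: "Good vs. poor quality TMS assessments will be evaluated as a measure of electrophysiologic response". SAP 3.8.3 then models it in a generalised version of the efficacy model, and applies to RMT, the key secondary endpoint, the same samples and models as to SICI.

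SAP 3.5 defines AllQual as "ALS participants and observations in the PP sample with no restriction that TMS quality is good". PP excludes observations made after permanent discontinuation and classifies by treatment received; mITT keeps those observations and classifies as randomised. SAP 3.8.2 commits to using the unfiltered sample: "AllQual sample: The primary efficacy model and the secondary random-slopes model and active vs. placebo estimand will be applied to the AllQual sample". Protocol 5.7 asks participants who stop study drug to keep attending visits.

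**The concern.** The primary estimate is defined on mITT, as randomised, but the values entering it are selected by a variable measured after randomisation that the SAP regards as a possible response to treatment. If recordability depends on SICI or RMT, or on both the outcome and the arm, the retained values are not a fair sample of the recorded ones. The natural check is to rerun the same model on the same sample without the filter. The plan makes that check only on PP, where the population and the grouping rule both differ from the primary analysis. A reader who wants to know whether the filter moved the primary result cannot find out from any listed run.

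**Working it through.** **1. The plan's own sample size.** SAP 3.4: difference 25, SD 30, two-sided alpha 0.027, 80% power, t-test. This needs 29 evaluable per arm; 29/(1 - 0.25) = 38.7, so 39 against the stated 40. At 40 x 0.75 = 30 evaluable, power is 82.8%. The figure reproduces. The 25% is for loss to follow-up, and no separate allowance for quality exclusions is stated.

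**2. Which analysis uses which record (SAP 3.5, 3.8.1, 3.8.2).**

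| Sample | Quality filter | After discontinuation | Grouping |
|---|---|---|---|
| mITT | on | kept | randomised |
| PP | on | dropped | received |
| loRMT (within PP) | on | dropped | received |
| AllQual (within PP) | off | dropped | received |
| not planned | off | kept | randomised |

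On-drug filtered records enter AllQual only. Post-discontinuation records that pass enter mITT only. Records that are both post-discontinuation and filtered enter no SICI or RMT analysis. Placebo multiple imputation, as described, replaces missing values and does not put recorded ones back.

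**3. How the filter relates to the endpoints (SAP 3.3.1).** SICI: "Paired-pulse SICI is defined as the ratio of the response after a conditioning pulse equal to 80% of RMT is administered 3 ms prior", divided by MEP amplitude at 120% of RMT. Neither CSP nor a fitted curve parameter enters the ratio, but CSP is elicited at the same 120% and the curve covers "MEPs elicited by stimuli ranging in strength from 60% of RMT to 150% of RMT". For RMT, the loRMT sample is restricted to records "with RMT less than 67% of maximum stimulator output. This criterion ensures that the full TMS input/output curve could be conducted": 1.5 x 67% = 100.5% of output.

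**4. Illustrative size for SICI.** All failure inputs are assumed.
- Log SD = sqrt(ln(1 + 0.30^2)) = 0.294, from the planned 100 (30); effect ln(0.75) = -0.288 or 0; intraclass correlation 0.5 (assumed).
- Two pre-treatment visits plus Weeks 6 and 8, filter applied at all four, shared-baseline model with a random participant intercept. Site effects, random slopes and Weeks 4 and 12 are left out.
- A visit fails on CSP or input/output when a latent quality score, with correlation rho to log SICI, falls in its lowest p. Here p = 2.5-22.5% (25-75% of a 10-30% total), with a further 5% failing at random.
- The drug lowers the latent score by 0, 0.5 or 1.0 SD.

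| Assumption | True 25% reduction read as | No effect read as |
|---|---|---|
| rho = 0 | 25% | 0 |
| rho +/-0.3 to +/-0.6, no drug effect on quality | 22-25% | 0 |
| same rho, 0.5 SD drug effect | 18.7-25.5% | 0.4-3.3% either way |
| rho +/-0.6, p = 22.5%, 1.0 SD drug effect | not tabulated | about 7-8% either way |

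Hand check of the null rows at p = 22.5%, rho = 0.6. The failure threshold is t = -0.755, and the shift in the retained mean is rho x SD x [h(t + d) - h(t)], where h is the normal density over the upper tail.
- d = 0.5: 0.6 x 0.294 x (0.643 - 0.387) = 0.045. Baseline adjustment in the model brings this to about 3%. Active-arm failure is Phi(-0.255) = 40%.
- d = 1.0: 0.6 x 0.294 x (0.960 - 0.387) = 0.101, brought to about 7-8%. Active-arm failure is Phi(0.245) = 60%.

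**5. What PP against AllQual leaves open.** Assume 10-30% of an active arm stop before Week 6, keep attending with no remaining effect, and 10-30% of records fail the filter. The filter's effect on the mITT estimate then differs from its effect on PP by 0-1.9 percentage points. The largest gap is -4.2 - (-2.3) = -1.9.

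**The case against.** The SAP already tests most of this. PP and AllQual share population and grouping and differ only in the filter, so their contrast isolates it for both endpoints on on-treatment data. The by-arm model of good quality would show whether exclusions differ by treatment. SAP 3.8.6 leaves room for further sensitivity models. What remains is a single analysis, and the gap of at most 1.9 points in step 5 is small and rests on assumed stopping and attendance. All of this stands, and it is why the point is minor.

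Stronger readings are tempting, and the documents do not support them:

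- **The whole-session rule is a mistake because CSP and the curve are irrelevant to SICI.** They share the 120% stimulus with the SICI denominator, so failure there can signal a poor session. A strict rule is a defensible pre-specified choice.
- **The drug affects recordability.** The SAP plans to examine this; it does not report it.
- **High RMT values are cut off.** That needs incomplete curves to be flagged poor, which the SAP does not say. The existence of loRMT within filtered PP data implies that some records at or above 67% pass. If 25-50% of records above 66.7% failed (assumed RMT mean 50-60, SD 10-12), a true rise of 3 or 5 points would be read 0-8% too small, with no bias under no effect.
- **The filter creates false positives.** With no true effect, bias needs failure to be related to SICI and also to differ by arm.

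**Conclusion.** The structural point holds: the plan has no mITT, as-randomised estimate of SICI or RMT on all recorded values, and the only unfiltered sample cannot supply one. Whether this matters numerically is unknown, because no failure rate or failure mechanism is given. If failure is unrelated to the outcomes, bias is nil. If it is related, the assumed cases with a 0.5 SD drug effect on quality read a true 25% SICI reduction as about 19-25%, so mainly attenuation, and no effect as up to about 3% either way. That 3% is not a ceiling: a 1.0 SD drug effect gives about 7-8%, but only with some 60% of active-arm visits failing. The filtered mITT analysis can remain primary. No gain in power is claimed, since the restored values may be noisier. Severity: minor.

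**What to change.** - Define AllQual on the mITT sample, or add one mITT all-quality run of the SAP 3.8.1 model for SICI and one for RMT, labelled as a sensitivity analysis. Keep the filtered mITT analysis as primary, and the PP-based AllQual if wanted.
- Tabulate excluded SICI and RMT records by reason (overall, RMT, input/output, CSP flag, CSP of zero), visit and arm, with RMT of 67% or more shown separately.
- Optional wording in SAP 3.5: state that eligible means eligible as determined at randomisation. Protocol 13.1 does not use the word, and Protocol 5.6 foresees enrolment errors found later. The sentence would make clear that dosed participants later found ineligible stay in the safety and mITT samples.

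Cost: one extra model run per endpoint, on possibly noisier values, one table from flags that already exist, and at most one sentence of text.
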